14.1.3 BLINDING

Participants, treating clinicians, and study personnel will be blinded to the assigned intervention group for each participant until after the database is locked and the blinded analysis is completed. Only the biostatistical team that is preparing closed interim reports will be unblinded. Specifically, TL will be delivered similarly to both active and placebo groups, but the circadian stimulus (the amount of light) will be different, albeit practically unidentifiable to participants; the light bulbs used to deliver the different light will be masked. Moreover, melatonin and its placebo control will be dispensed with packaging and labeling that will blind assignment. Unblinding will occur only if required for participant safety or treatment, at the request of the treating clinician. Refer to the MOP for further details.

14.2 ADDITIONAL APPENDIX-LEVEL EXCLUSION CRITERIA

The following additional exclusion criteria are to be considered together for determining eligibility. They are separated here by TL and melatonin only for presentation. RESET-PASC presents no additional exclusions.

14.2.1 TAILORED LIGHTING EXCLUSION CRITERIA

- 1. Severe visual impairments affecting sensitivity or ability to respond to light
- 2. Severe photosensitivity dermatitis
- 3. Severe progressive retinal disease, eg, macular degeneration
- 4. Permanently dilated pupil, eg, following certain cataract surgeries
- 5. Unwilling to remove or not wear blue-light-blocking glasses during TL dosing

14.2.2 MELATONIN EXCLUSION CRITERIA

1. Sleep medication, if not willing to washout for 4 weeks. Please see the MOP for a detailed list of prohibited medications.

14.3 HALTING RULES

Study drug dosing and enrollment will be temporarily suspended pending review of the DSMB if three or more participants receiving either active intervention experience an SAE of the same type that is determined to be related to the intervention. The DSMB recommendations will be considered by the NIH and the study principal investigator prior to making any decisions regarding study continuation or discontinuation.

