6.2 PREPARATION/HANDLING/STORAGE/ACCOUNTABILITY

6.2.1 ACQUISITION AND ACCOUNTABILITY

The use of study intervention will be tracked by the sites. The sites will call participants at least once during the intervention period to monitor compliance with study intervention administration.

For appendices with a study drug, receipt and use will be handled, tracked by the sites, and stored in a safe and secure location to which only the site investigator and designated personnel have access. Participants will also be asked to bring any unused study drug with them to the End of Intervention Clinic Visit, as applicable.

For appendices with a study device, receipt and use will be accounted for by the sites. Additionally, some devices may have accountability measures built in.

See appendices for further details.

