9.1.2 COLLECTION PERIOD OF AE AND SAE INFORMATION

Safety event collection will occur at the pre-specified study visits but all participants will be instructed to self-report concerns by calling the site.
Serious adverse events (SAEs), UADEs, or ESIs (per appendix) will be extracted by site personnel from the participant's medical record if the participant seeks medical care or if hospitalization occurs, each of which notifies the site to conduct follow-up.

Medical occurrences that begin before the first invasive study procedure (blood collection or nasal swab), but after obtaining informed consent, will not be considered an AE. The medical occurrence or condition will be captured on the Medical History electronic case report form (eCRF).

Non-serious AEs may be reported by the participant, but will not be collected into the study database as an AE or further assessed by the site or study personnel. Non-serious AEs that result in study intervention discontinuation will be identified as the reason for study intervention discontinuation in the study database and reported separately as an AE, and they will be collected from the start of study intervention administration through the end of the intervention.

Any AEs that are also classified as symptoms associated with PASC and collected during the study will not be collected as a safety event to the study database or further assessed by the site or study personnel because they will be collected as part of the PASC symptom dataset.

Serious adverse events (SAEs) will be collected from the first invasive study procedure (blood collection or nasal swab) through the End of Study for all appendices that use a study drug and through the EOI Clinic Visit for all appendices that include other interventions.

UADEs will be collected in the clinical database from the start of the intervention through the end of the intervention.

Adverse events (AEs) that qualify as an ESI, even if a non-serious AE, will be collected from the start of the study intervention through the End of Study (30 ± 3 days after EOI) for all appendices that use a study drug and through the EOI Clinic Visit for all appendices that include non-drug interventions.

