9.1.4 REPORTING AND MONITORING OF SAES FOR STUDY DRUG(S) OR UADES FOR DEVICE(S)

Study drugs used in this platform protocol are not approved for the indication for the treatment of PASC. The DSMB will review aggregate safety data according to the DSMB Charter.

Any UADE(s) that a platform protocol principal investigator determines is/are reportable will be submitted to the manufacturer, all reviewing IRBs, and all participating site investigators within 10 working days of when the platform protocol principal investigator makes that determination.

If the platform protocol principal investigator determines that a UADE presents an unreasonable risk to participants, all investigations or parts of investigations presenting that risk shall be terminated as soon

as possible. Termination shall occur no later than 5 working days after the sponsor makes this determination and no later than 15 working days after the sponsor first received notice of the effect.

Individual SAEs or UADEs must be entered into the data system within 24 hours of site awareness. After receiving that data, within 1 to 2 business days the DCRI Safety Surveillance team will notify pharmaceutical partners of SAEs (if applicable) and device manufacturers of UADEs that occur involving the specific appendix of the supplied study drug/control or supplied device, as required.

Serious adverse events (SAEs) that are related to the study drug and confirmed unlisted by the DCRI Safety Medical Monitor and platform protocol principal investigator will be reported to the central IRB as SUSARs — as 7-day reports for unexpected fatal or life-threatening adverse reactions and 15-day reports for serious and unexpected adverse reactions. The SUSARs will be shared with the pharmaceutical partner of the supplied study drug according to the same timelines, if applicable. If the DSMB notes a clinically important increase in the rate of a SUSAR, the platform protocol principal investigator will notify site investigators no later than 15 calendar days after determining that the information qualifies for reporting. The site investigators will notify their local IRBs according to local guidelines, if applicable. Refer to the Safety Management Plan for details regarding specific reporting timelines.

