11.1.2 STUDY DISCONTINUATION AND CLOSURE

This study may be temporarily suspended or prematurely terminated if sufficient reasonable cause exists. Written notification, which documents the reason for study suspension or termination, will be provided by the sponsor to study participants, site investigators, the central IRB, and the US FDA. Study participants will be contacted, as applicable, and be informed of changes to the study visit schedule.

Circumstances that may warrant termination or suspension include, but are not limited to, the following:

- Determination of futility
- Determination of unexpected, significant, or unacceptable risks to participants
- Insufficient compliance with protocol requirements
- Data that are not sufficiently complete and/or evaluable

The study may resume once concerns about safety, protocol compliance, and data quality are addressed, and satisfy the sponsor, IRB, and/or FDA.

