13.3 HALTING RULES

Study drug dosing and enrollment will be temporarily suspended pending review of the DSMB if 3 or more participants on the same study drug within Appendix A experience an SAE of the same type that is determined to be related to the study drug. The DSMB recommendations will be considered by the NIH and the study Principal Investigator prior to making any decisions regarding study continuation or discontinuation.

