14 APPENDIX B: COMPLEX PASC-RELATED SLEEP DISTURBANCES (CPSD)

14.1 STUDY DESIGN AND RATIONALE

The Complex PASC-Related Sleep Disturbances (CPSD) Appendix B combines brief education and a tailored sleep timing prescription for CPSD (referred to as RESET-PASC) with therapies that modify circadian timing for participants who report poor sleep quality or daytime sleep-related impairment. The intervention therapies involve tailored lighting (TL) and melatonin. Participants will be randomly assigned to one of four groups: (a) active TL + oral melatonin, (b) active TL + placebo melatonin, (c) placebo TL + oral melatonin, and (d) placebo TL + placebo melatonin. All groups will receive RESET-PASC. The 2x2 factorial design schema is shown in Figure 5. The intervention duration will be 9 weeks.

Figure 5. Appendix B 2x2 Factorial Design

		Pharmacologic Intervention						
_		Melatonin	Placebo					
imenta ention	Light	Melatonin + Light	Placebo + Light					
Environmental Intervention	Placebo Light	Melatonin + Placebo light	Placebo + Placebo light					
_	Reset-PASC							

PASC can lead to complex sleep disturbances that present similarly to but have overlapping qualities of known types of disturbed sleep, such as insomnia and circadian rhythm/sleep-wake disorders. Both types of sleep disturbances affect one's ability to sleep at night, and many patients with PASC present with symptoms of both insomnia and sleep-wake rhythm disturbances, suggesting common underlying mechanisms. Intervention strategies for the two conditions often overlap. Thus, the interventions in this study target common underlying mechanisms and represent the typical, real-world approaches for treating patients with complex sleep disturbances.

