14.6 RESET-PASC INFORMATION

RESET-PASC will involve providing participants with education on healthy sleep behaviors through short videos (and/or paper brochures); a tailored prescription for timing of bedtime, light and melatonin/ placebo use; and electronic messages to reinforce sleep timing. Educational videos will be accessed by the participant at the beginning of the intervention period. A central investigator will review each participant's survey data remotely and will develop an initial prescription for when the participant should be exposed to the tailored light/sham light, when he/she should take melatonin/placebo, and when the participant should go to bed. This prescription will be communicated to the participant during a telephone call by a central investigator. After the initial "sleep prescription," the participant will be contacted by telephone or text message approximately every 2 weeks for 6 weeks to reinforce (or troubleshoot) light and drug/placebo adherence and bedtime routines. To inform recommendations, a central team will review responses from periodic electronically distributed questionnaires (SASS-Y, PGIC). The central team assessing the surveys will be blinded to the participant's intervention allocation.

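### Appendix B's halting rule can be triggered by SAEs related to tailored light, but its automatic action pauses only study drug dosing and enrollment, not lamp use by enrolled participants

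*Protocol*

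**What the plan says.** Appendix B is a 2x2 factorial comparison. Section 14.1 states: "The intervention therapies involve tailored lighting (TL) and melatonin". Its halting rule (14.3) reads: "Study drug dosing and enrollment will be temporarily suspended pending review of the DSMB if three or more participants receiving either active intervention" have an SAE of the same type that is judged related to the intervention.

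The Appendix A rule (13.3) prescribes the same action, but its trigger is confined to drugs: "if 3 or more participants on the same study drug within Appendix A experience an SAE of the same type". Section 7.4 of the platform protocol contains no rule of its own and refers to the appendices, so 14.3 is the only fixed-count safety pause that applies to Appendix B.

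**The concern.** A halting rule with a fixed count exists so that exposure to a suspected cause stops first and deliberation follows. In 14.3 the events that set the rule off and the exposures it switches off are not the same set. Light is in the first and absent from the second. If the signal came from the lamp, the rule would pause the capsules, which are not implicated, and say nothing about the lamp.

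The lamp would then tend to stay in use. It runs on a timer set to the desired wake time (14.4.2), interventionists phone to encourage light adherence (14.4.3), and participants are contacted about every two weeks to "reinforce (or troubleshoot) light and drug/placebo adherence and bedtime routines" (14.6). At stake is continued exposure of enrolled participants during DSMB review.

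**Working it through.** The rule's only number is the count of three participants, which is not in dispute. The check is mainly a comparison of texts.

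**1. Scope of the trigger.** Either active intervention (14.3), meaning tailored light or melatonin (14.1).

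**2. Scope of the action.** Study drug dosing and enrollment (14.3).

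**3. Does study drug include the lamp?** The protocol separates the terms:
- 6.2.1 has one paragraph for study drugs and another for devices: "For appendices with a study device, receipt and use will be accounted for by the sites".
- 9.1.2 sets the collection period for events of special interest separately: "for all appendices that use a study drug and through the EOI Clinic Visit for all appendices that include non-drug interventions".
- The heading of 9.1.4 sets drugs apart from devices.
- Within Appendix B, 14.6 names light and drug/placebo as two things.

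The word dosing is used for light in 14.2.1 and 14.4.3. In 14.3, however, it is qualified as study drug dosing, which does not reach the lamp.

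**4. Result by type of trigger.**

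| SAEs judged related to | Rule triggered | Capsules | Enrollment | Lamp in enrolled participants |
|---|---|---|---|---|
| Melatonin | yes | paused | paused | no instruction |
| Tailored light | yes | paused | paused | no instruction |

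The second row is the gap.

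**5. Other ways to stop the lamp.**
- UADE termination (9.1.4) requires the platform principal investigator to determine that the risk is unreasonable. Action is then due as soon as possible, with an outer limit of "no later than 15 working days after the sponsor first received notice of the effect".
- Study suspension (11.1.2) lists among its possible grounds: "Determination of unexpected, significant, or unacceptable risks to participants". It is permitted, not required.
- Discontinuation of an individual participant (7.1) is at the site investigator's discretion.

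None of these follows automatically from the 14.3 count.

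**6. Bound on uncovered exposure.** Light is delivered for 8 weeks (14.4.3): 8 × 7 = 56 days, at least one hour each morning. Let T be the days from trigger to DSMB review and d the days of the light course already completed. Further lamp days are at most

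E = min(T, 56 − d).

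T is not given. Section 10.4.5 allows extra meetings or calls, so I assume 7 to 21 days:
- T = 7, d = 0: E = 7, and 7/56 = 12.5% of the course.
- T = 21, d = 0: E = 21, and 21/56 = 37.5%.
- d = 53: E = 3 for either T, and 3/56 = 5.4%.

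If review waited for a quarterly meeting, T could reach 365.25/4 = 91.3 days (13.0 weeks). That exceeds 56, so E would be whatever remained of the course. An earlier call is more likely.

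The UADE outer limit in calendar days, ignoring holidays, is 15/5 × 7 = 21, again at most 37.5% of the course.

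The number of participants using a lamp at a trigger cannot be derived, because accrual is not stated.

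**The case against.** The strongest case on the other side concerns weight:

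- Three same-type SAEs, each judged related to a plug-in white-light lamp, are improbable. Section 14.4.1 rates the light non-significant risk and names only headache, as a rare effect. Section 14.7 lists no events of special interest. This stands and limits the importance of the point.
- The device route can open earlier than 14.3. Under 9.1.1, a serious lamp-related event not already identified could qualify as a UADE at the first case, not the third, and 9.1.4 requires entry within 24 hours. This also stands. But termination still depends on a finding of unreasonable risk, and a serious headache might not qualify under criterion A because headache is already listed.
- The 14.3 trigger itself needs judgement on relatedness and event type. True, but once it is met the pause is fixed, whereas the other routes remain optional.

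A reader might infer more than the text supports:

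- That a light signal leaves participants with no protection. It does not: enrollment stops, the DSMB reviews, and three discretionary routes remain.
- That the protocol intends lamp use to continue. Section 14.3 is silent on light. The wording may have been carried over from 13.3, but that is conjecture and the point does not depend on it.
- That every light user would have 7 to 21 further sessions. Those figures rest on an assumed review time and are maxima for people with enough of the course left. Placebo lamps also deliver a stimulus below the activation threshold (14.4.3), so lamp use is not always active exposure.

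**Conclusion.** The mismatch is plain on the face of 14.3: light can trigger the rule, and the rule's automatic action does not reach light. The omission is in a complete sentence of a safety rule that sites must apply as written; it is not a detail that would normally be left to a statistical analysis plan.

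The practical weight is minor to modest. The light carries low stated risk, enrollment stops, and the gap closes at DSMB review or at the end of the participant's 56-day course, whichever comes first. The conclusion on scope needs no numerical assumption. The 12.5% and 37.5% figures rest on an assumed review time of 7 to 21 days and a participant at the start of the course.

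Pausing every lamp after a clearly melatonin-only trigger is not needed to close the gap. It would interrupt light treatment without a light signal.

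**What to change.** In 14.3, replace the opening subject of the sentence with: *Use of the implicated study intervention (melatonin/placebo capsules and/or tailored/placebo light; both if attribution is uncertain) and enrollment*. The rest of the sentence can stay, and 13.3 needs no change.

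Applying the pause to active and placebo versions alike lets sites, who are blinded to both factors (14.1.3), carry it out without unblinding. The clause on uncertain attribution matters because one of the four groups receives both active interventions.

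The cost is one phrase, an instruction to enrolled participants to stop using the lamp, and a temporary interruption of light after a light-related or unattributed trigger. Capsules would also no longer stop automatically after a trigger clearly due to light alone, which is a narrower action than the present text.

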14.4 TAILORED LIGHT INFORMATION

14.4.1 RISK ASSESSMENT

Tailored Light (TL) is considered non-significant risk. Side effects of TL have not been extensively reported. A rare side effect is headache. Further, participants may be withdrawn at the investigators' discretion.

14.4.2 LIGHT DELIVERY METHOD

The modified table/floor lamp will deliver polychromatic white light from up to 12-16 inches from the open eye for at least 1 hour in the morning (within 2 hours of waking, but no later than noon). The table/floor lamp is a controlled plug-in fixture that will be placed on a timer. The timer will be set to turn the light table on at desired wake times and turn it off 4 hours before desired bedtimes.

Participants will also wear a light sensor (Blue Iris Labs Mobile Sensor) to measure existing surrounding lighting during the intervention. The Blue Iris is a personal light meter calibrated to measure circadianeffective light. It can store 60 days of light measurements at 1-min intervals. It will characterize the light exposure of each participant. This light sensor will help verify compliance with the light exposure protocol. Importantly, the Blue Iris is noninvasive, not a medical device, and produces no harmful emissions. Similar to wearing a badge, participants will be asked to wear the device for the duration of the study, but at a minimum for 7 days after TL installation and 7 days before EOI. If they choose not to wear the Blue Iris device for the duration of the study, they will be asked to keep a daily log with the start and end times they were exposed to the intervention.

14.4.3 DOSING

The table/floor lamp will provide a circadian stimulus equal to 0.3 at the cornea,⁶¹ and will be delivered for 8 weeks.

Placebo delivery will be through the same lamp method; however, it will be programmed to deliver a circadian stimulus less than 0.1, which is below the threshold for activating the circadian system. This will be accomplished by utilizing a low brightness bulb.

Light from the table/floor lamp must be delivered within 2 hours of waking for at least 1 hour. Lamp use greater than 1 hour during the daytime hours (between desired wake times and 4 hours before desired bedtime) will be encouraged.

The table/floor lamp will be programmed to be turned off 4 hours before desired bedtimes.

Participants will be encouraged to minimize exposure to all ambient and device-related light, including from electronic devices and daylight, 1 hour before their scheduled bedtime.

Interventionists will call participants throughout the intervention to encourage light adherence.

14.4.4 RATIONALE FOR SELECTION OF DOSE

Tailored lighting in the morning will produce light levels (circadian stimulus = 0.3) at least 5 to 10 times higher than typical household evening light, thereby ensuring a high circadian light-entrainment contrast between day and night. This amount of circadian stimulation is effective at entraining the circadian system and improving sleep when delivered during the daytime.^{62,63} Morning doses of light are associated with strengthening circadian rhythms and improving sleep. Additionally, individuals with bright compared to dim indoor lighting report fewer sleep disturbances, which is similar to individuals who spent at least 1 hour outdoors compared to those spending 15 minutes or less.⁶² Tailored lighting options delivering a circadian stimulus of 0.3 will deliver at least 300 to 400 lux at the eye at the suggested times in the morning. This dose delivered for 1 hour is equivalent to a nocturnal melatonin

suppression by 30%, suggesting that this dose can affect the biological clock.⁶⁴ Greater amounts of daytime light have been shown to increase melatonin production during the nighttime.⁶⁵

14.5 MELATONIN INFORMATION

14.5.1 RISK ASSESSMENT

Melatonin AEs are rare. The only one occurring at a frequency greater than 1% is daytime sleepiness at 1.66%.⁶⁶ Adverse events occurring less than 1% include, but are not limited to, headache and dizziness. The presence of at least one of the above-mentioned mild symptoms was about 6% more common in people who took melatonin than those who took the placebo. Melatonin presents no significant safety risks in adults. Further, participants may be withdrawn at the investigators' discretion.

Expected AEs are those listed in the protocol appendix.

